**5.7.4. Adjustment for Multiple Comparisons**

To control the overall Type I Error of the clinical trial at 5%, the graphical testing procedure (Bretz 2009) will be applied. The order the hypothesis will be tested is provided in the schematic representation of the multiple testing procedure below (Figure 2).

If a hypothesis is rejected, the alpha level for that hypothesis will be reallocated to other hypothesis according to the graph. The graph will be updated according to the pre-specified algorithm, as described by Bretz 2009. The rest of the hypotheses will be tested at the updated alpha level based on the updated graph. The testing will stop when no hypothesis can be rejected at any step.

**Figure 2: Hypothesis Testing Procedure**

### 5.7.5. Analysis of Other Efficacy Variables

As additional sensitivity analyses, the following efficacy endpoints will be analyzed using the same method as was used for hypotheses  $H_{1,1}$ , and  $H_{2,1}$ :

- Change in WOMAC pain subscale scores from baseline to week 48
- Change in WOMAC physical function subscale scores from baseline to week 48
- Change in WOMAC pain subscale scores from baseline to week 52
- Change in WOMAC physical function subscale scores from baseline to week 52

The same analysis used for hypotheses  $H_{1,3}$ ,  $H_{1,16}$ , and  $H_{2,3}$  will be used to analyze the following additional efficacy endpoints:

- The number and percentage of patients with an improvement of  $\geq 50\%$  from baseline in the WOMAC pain subscale scores at weeks 16, 44, 52
- The number and percentage of patients with an improvement of  $\geq 70\%$  from baseline in the WOMAC pain subscale scores at week 16, 44, 52
- The number and percentage of patients with an improvement of  $\geq 30\%$  from baseline in the WOMAC physical function subscale scores at week 16, 44, 52
- The number and percentage of patients with an improvement of  $\geq 50\%$  from baseline in the WOMAC physical function subscale scores at week 16, 44, 52
- The number and percentage of patients with an improvement of  $\geq 70\%$  from baseline in the WOMAC physical function subscale scores at week 16, 44, 52
- The number and percentage of patients meeting the OMERACT-OARSI criterion at week 16, 44, 52

Cumulative distribution of percent change from baseline to Week 16 in the WOMAC pain and physical function scores will be presented by treatment group. The cumulative distribution plot displays a continuous plot of the percent change from baseline on the X-axis and the percent of patients experiencing that change on the Y-axis.

#### Walking Index Joint Pain Questionnaire

Analysis of the WIIPNRS pain scale will be on the weekly averages. Baseline is defined as the average of the non-missing values during 7 days prior to taking study drug. For each week, the average of the non-missing values during the 7 days on or prior to that week will be used. If all values are missing for the 7 days, the value for that week is set to missing. The MMRM model will include the randomization strata (K-L category [2-3 vs. 4], index joint [hip or knee] and geographic region [North America, Europe]), treatment, week (weeks 1, 2, ..., 52), treatment-by-week interaction as fixed effects, and baseline average NRS value as a covariate. The least-squares (LS) means for the mean change from baseline to each week, as well as the LS mean differences between fasinumab doses and placebo, with their corresponding standard errors (SEs), p-values and associated 95% confidence intervals, will be provided from the MMRM. If the model does not converge using unstructured covariance matrix, an autoregressive 1 covariance structure will be used.

### Rescue Medications

The number (and percentage) of patients using rescue medication during the Pre-Treatment Period will be summarized by treatment group and overall based on the SAF – Year 1 and SAF – Year 2. Analogous analysis will be performed for both the Year 1 On-Treatment Period and Year 2 On-Treatment Period based on the SAF – Year 1 and SAF – Year 2 respectively.

For patients taking rescue medication, descriptive statistics of the number of days patients took rescue medications will be presented by treatment group during both the Year 1 On-Treatment Period and Year 2 On-Treatment Period based on the SAF – Year 1 and SAF – Year 2 respectively.

For patients taking rescue medication, weekly average usage of rescue medications (measured in mg) is calculated as follows:

$$= \frac{\text{Total amount of rescue medication used in the specified week (in mg)}}{\text{number of diary entries in the specified week}}$$

Descriptive statistics of the weekly average usage of rescue medications will be presented by treatment group for both the Year 1 On-Treatment Period and Year 2 On-Treatment Period based on the SAF – Year 1 and SAF- Year 2 respectively..

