#### 4.2.3. Exploratory Endpoints

The exploratory endpoints in the study are:

1. Change from baseline to weeks 16 and 44 in patient-reported outcome measures in patients with pain due to OA of the knee or hip treated with fasinumab compared to placebo

- 2. Change from baseline to weeks 16 and 44 in patient-reported outcome measures in patients with pain due to OA of the knee or hip treated with fasinumab compared to naproxen
- 3. The proportion of patients taking rescue medication, number of days on rescue medication, and weekly average use of rescue medication from baseline to weeks 16 and 44 in patients with pain due to OA of the knee or hip treated with fasinumab compared to placebo
- 4. The proportion of patients taking rescue medication, number of days on rescue medication, and weekly average use of rescue medication from baseline to weeks 16 and 44 in patients with pain due to OA of the knee or hip treated with fasinumab compared to naproxen
- 5. Percentage of patients treated with fasinumab, compared with that of patients treated with placebo, who had improvements of ≥50% and ≥70% in the WOMAC pain subscale scores at weeks 16 and 44
- 6. Percentage of patients treated with fasinumab, compared with that of patients treated with placebo, who had improvements of ≥30%, ≥50% and ≥70% in the WOMAC pain subscale scores at weeks 16 and 44
- 7. Percentage of patients treated with fasinumab, compared with that of patients treated with placebo who met the OMERACT-OARSI criterion at weeks 16 and 44
- 8. Descriptive analyses of the change from baseline at all visits from weeks 52E and 104E of the WOMAC pain and physical function subscale scores in patients with pain due to OA of the knee or hip treated with fasinumab compared to naproxen prn
- 9. Descriptive analyses of the change from baseline at all visits from weeks 52E and 104E in patient-reported outcome measures in patients with pain due to OA of the knee or hip treated with fasinumab compared to naproxen prn
- 10. The proportion of patients taking rescue medication, number of days on rescue medication, and weekly average use of rescue medication from weeks 52E to 104E in patients with pain due to OA of the knee or hip treated with fasinumab compared to placebo

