#### 7.3.2. Study Drug Discontinuation

Study drug may be temporarily or permanently discontinued due to medical need, as determined by the investigator or the Sponsor and according to the study stopping rules (Section 5.1.8).

Patients who permanently discontinue from study drug will be encouraged to remain in the study and to complete all study procedures and assessments including completion of the diary, the only exception being not receiving study drug (oral and SC). Patients must continue to adhere to the prohibited medication list as per Section 7.7.1. Patients who agree and thus do not withdraw from the study will be asked to return to the clinic for all remaining study visits per Table 1.

Patients who permanently discontinue from study drug and who opt to withdraw from the study will be asked to complete early termination study assessments, per Table 1.

Patients who discontinue from study drug prior to study completion due to an AA (see Section 9.6.1.1) should return to the clinic for all remaining study visits per the visit schedule.

In the event that a patient must undergo JR surgery during the treatment or follow-up periods, he/she will be discontinued from study drug and asked to return to the study site for a pre-operative visit and for follow-up safety evaluations (as described in Section 8.2.3.10) 4 and 20 weeks after surgery. Pre-operative imaging (X-ray and MRI) will be obtained and submitted to the independent adjudication committee for review to ensure that an AA event is not in occurrence. Instructions for the submission process are provided in the study manual.

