## 2.2. Sample Size and Power Considerations

In this study, approximately 2560 patients were planned to be randomized to fasinumab 1 mg SC Q4W (840), fasinumab 1 mg SC Q8W (600), naproxen (840), or placebo (280) (see Section 5.1.3 of the protocol). This sample size was expected to provide adequate power for the comparisons between fasinumab and naproxen at week 16 for the WOMAC pain and physical function scores and the Patient Global Assessment - Osteoarthritis (PGA-OA) score and provide long term data for safety assessment.

The sample size was based on results of the WOMAC pain and physical function subscale scores and the PGA from the R475-PN-1227 study. The calculation of sample size assumed a 2-sided alpha level of 0.025 and a 15% dropout rate up to week 16 and a 30% dropout rate up to week 52. Enrollment of 840 patients in the fasinumab 1 mg Q4W group and 280 patients in the placebo group would have provided at least 99% power to detect an effect size of 0.46 in the WOMAC pain and physical function subscale scores (i.e., an absolute treatment difference of 1.1 between fasinumab and placebo and a standard deviation [SD] of 2.4 at week 16 and 52 for the full analysis set [FAS]). This sample size would have provided 99 % power to detect an effect size of 0.36 in PGA for an absolute treatment difference of 0.4 with a SD of 1.1 at week 16, and 98% power at week 52 for the FAS.

For the fasinumab 1 mg Q8W group, the 600 patients would have been compared to the approximately 200 patients in the placebo group who were enrolled after Protocol R475-OA-1611 Amendment 5 Global was implemented. For such comparisons, 2-sided alpha level of 0.025 and a 15% dropout rate up to week 16 and a 30% dropout rate up to week 52 were assumed. Additionally, the effect size for such comparisons were assumed to be 80% of the effect size for the comparison between fasinumab 1 mg Q4W group and the placebo group. Under these assumptions, enrollment of 600 patients in the fasinumab 1 mg Q8W group and 200 patients from the placebo group would have provided 97% power to detect an effect size of 0.368 ( $=0.46*80%$ ) in the WOMAC pain and physical function subscale scores at week 16 and 93% power at week 52. This sample size would have provided 84% power to detect an effect size of 0.288 ( $=0.36*80%$ ) in PGA at week 16, and 75% power at week 52 for the full analysis set (FAS).

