### 4.5.3. Exploratory Variables

The exploratory endpoints in the study are

1. Change from baseline to week 16 and 44 in patient-reported outcome measures in patients with pain due to OA of the knee or hip treated with fasinumab compared to placebo
2. Change from baseline to week 16 and 44 in patient-reported outcome measures in patients with pain due to OA of the knee or hip treated with fasinumab compared to naproxen
3. The proportion of patients taking rescue medication, number of days on rescue medication, and weekly average use of rescue medication from baseline to week 16 and 44 in patients with pain due to OA of the knee or hip treated with fasinumab compared to placebo
4. The proportion of patients taking rescue medication, number of days on rescue medication, and weekly average use of rescue medication from baseline to week 16 and 44 in patients with pain due to OA of the knee or hip treated with fasinumab compared to naproxen
5. Percentage of patients treated with fasinumab, compared with that of patients treated with placebo, who had improvements of  $\geq 50\%$  and  $\geq 70\%$  in the WOMAC pain subscale scores at week 16 and 44
6. Percentage of patients treated with fasinumab, compared with that of patients treated with placebo, who had improvements of  $\geq 30\%$ ,  $\geq 50\%$  and  $\geq 70\%$  in the WOMAC pain subscale scores at week 16 and 44
7. Percentage of patients treated with fasinumab, compared with that of patients treated with placebo who met the OMERACT-OARSI criterion at week 16 and 44
8. Change from baseline at all visits from week 52E and 104E of the WOMAC pain and physical function subscale scores in patients with pain due to OA of the knee or hip treated with fasinumab compared to naproxen prn
9. Change from baseline at all visits from week 52E and 104E in patient-reported outcome measures in patients with pain due to OA of the knee or hip treated with fasinumab compared to naproxen prn
10. The proportion of patients taking rescue medication, number of days on rescue medication, and weekly average use of rescue medication from week 52E to week 104E in patients with pain due to OA of the knee or hip treated with fasinumab compared to placebo
11. The proportion of patients taking rescue medication, number of days on rescue medication, and weekly average use of rescue medication from week 52E to week 104E in patients with pain due to OA of the knee or hip treated with fasinumab compared to naproxen

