## 5. STATISTICAL METHODS

For continuous variables, descriptive statistics will include the following: the number of patients reflected in the calculation (n), mean, median, standard deviation, minimum & maximum and 1st & 3rd quartiles (Q1 & Q3).

For categorical or ordinal data, frequencies and percentages will be displayed for each category.

**Period of observation** – Unless otherwise stated, analysis of all safety variables captured at multiple visits will be analyzed by the following observations periods:

- The Pre-Treatment Period is defined as the time from signing the ICF to before the first dose of study drug in Year 1.
- The Year 1 On-Treatment Period is defined as the day from first dose of Year 1 study drug through the day of last Year 1 SC dose + 4 weeks for those patients not proceeding into Year 2, or up to the first dose of Year 2 study drug for those patients proceeding into Year 2. Summaries for the Year 1 On-Treatment Period will be based on the SAF – Year 1.
- The Year 1 Post-Treatment Period is defined from the end of the Year 1 On-Treatment Period to the Week 72/Early Termination Visit for those patients not proceeding into Year 2. Summaries for the Year 1 Post-Treatment Period will be based on the SAF – Year 1.
- The Year 2 On-Treatment Period is defined as the day from first dose of Year 2 study drug through the day of last Year 2 SC dose + 4 weeks for those patients proceeding into Year 2. Summaries for the Year 2 On-Treatment Period will be based on the SAF – Year 2.
- The Year 1 and 2 On-Treatment Period is defined as day from first dose of Year 1 study drug through the day of last SC dose + 4 weeks. Summaries for the Year 1 and 2 On-Treatment Period will be based on both the SAF – Year 1 and SAF-Year 2.
- The Year 2 Post-Treatment Period is defined from the end of the Year 2 On-Treatment Period to the Week 124E/Early Termination E Visit for those patients proceeding into Year 2. Summaries for the Year 2 Post-Treatment Period will be based on the SAF – Year 2.

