### Footnotes for the Schedule of Events Table 3 (Year 1)

1. Patients who discontinue study drug before week 52 will be encouraged to follow the visit schedule through the remainder of the study. If a patient chooses to end study participation, he/she will be asked to return to the clinic as soon as possible for an early termination visit. Imaging assessments need to be repeated if it has been >30 days since the joints were last imaged. If it has been ≤30 days since imaging assessments were completed, imaging assessments may be completed at the discretion of the investigator.
2. HIV and/or hepatitis testing will be performed on a country-by-country basis, according to local guidelines if required by regulatory authorities or ethics boards.
3. Only for patients who provide written informed consent for the optional genomics sub-study. The sample should be collected at the day 1 (baseline/randomization) visit, but may be collected at any visit during the study after a patient has been randomized.
4. At the screening and pre-randomization visits, study staff will review the “Participating in a Research Study: What You Need to Know” brochure and the “Reporting Your Pain” brochure with patients to ensure they understand what a clinical study is and how to report their pain accurately. At subsequent visits, patients will be asked to review the “Reporting Your Pain” brochure themselves. At any time during the conduct of the study, patients may require retraining by study staff.
5. Subcutaneous study drug administration will be the last procedure at each dosing visit and will be administered after all laboratory, PK, ADA and research samples have been collected and all study related activities have been performed. Patients will be observed in the clinic for approximately 1 hour after SC study drug is administered.
6. Use of study-provided rescue medication will be recorded daily in patient diaries. Acetaminophen/paracetamol use will be reported from pre-randomization visit to week 52.
7. Patients will complete the WOMAC pain subscale for both hips and knees at the screening visit. Then, the WOMAC Full Survey will be completed only for the index joint at the subsequent visits.
8. Walking index joint pain NRS score will be recorded by the patient each day using their diary, starting during the pre-randomization period through week 52. Walking index joint pain NRS score will be recorded by the patient at the site at the week 52 visit.

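### The SAP reports the proportion using rescue medication and the number of rescue days only over each patient's own on-treatment period, so the Week 16 and Week 44 values that the endpoints name are not produced and the day count mixes use with time observed

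*SAP*

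**What the plan says.** SAP 4.5.3 lists, for fasinumab against placebo and against naproxen, three rescue components: the proportion of users, and "number of days on rescue medication, and weekly average use of rescue medication from baseline to week 16 and 44". Protocol 4.2.3 has the same endpoints with the same time frame.

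The analysis text is in SAP 5.7.5 under Rescue Medications.

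- **Proportion of users:** number and percentage of patients, for the Year 1 On-Treatment Period.
- **Number of days:** for patients taking rescue, "descriptive statistics of the number of days patients took rescue medications will be presented by treatment group during both the Year 1 On-Treatment Period", with the same for Year 2.
- **Weekly average:** total mg used in the week divided by "number of diary entries in the specified week".

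SAP section 5 defines the Year 1 On-Treatment Period, for patients who do not enter Year 2, as "the day from first dose of Year 1 study drug through the day of last Year 1 SC dose + 4 weeks". For those who continue, it ends at the first Year 2 dose.

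On data collection, a footnote to the Year 1 schedule in the SAP states that "Acetaminophen/paracetamol use will be reported from pre-randomization visit to week 52". Protocol 7.3.2 encourages patients who stop study drug to stay in the study and "to complete all study procedures and assessments including completion of the diary".

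**The concern.** There are two separate faults.

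First, the endpoint and its analysis use different time windows. Responder endpoints in the same SAP section are given at Weeks 16, 44 and 52; the rescue proportion and rescue days are not given at Week 16 or 44. SAP 5.7.7 repeats the same analyses on the FAS and the efficacy table in SAP 10.1 has no rescue row, so neither supplies the missing time points. Nothing in the SAP marks the change of window as deliberate.

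Second, a count of days over a window that ends when treatment ends is partly a measure of how long treatment lasted. A heavy user who stops early can rank as a light user.

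What is at stake is interpretation. The primary estimand in SAP 5.7.1 takes WOMAC scores regardless of rescue use, so rescue use by arm up to Week 16 is natural context for the Week 16 pain result, and rescue use up to 44 weeks is a stated exploratory objective.

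**Working it through.** The documents state no figure for rescue days, so there is none to reproduce. The check is on what the planned derivation returns.

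**Window length.** SC doses are scheduled at Days 1, 29, ..., 337 (13 doses). Using the SAP 5.6.2 exposure convention, window = (day of last dose − 1) + 28.

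- 1 dose: (1 − 1) + 28 = 28 days
- 2 doses: (29 − 1) + 28 = 56 days
- 4 doses: (85 − 1) + 28 = 112 days
- 13 doses: (337 − 1) + 28 = 364 days

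The range is 364/28 = 13-fold. Visit windows of ±7 days shift these values slightly.

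**Against the stated time points.** Week 16 is Day 113 (112 days) and Week 44 is Day 309 (308 days). A completer with steady use accumulates 364/112 = 3.25 times as many days over the full period as to Week 16, and 364/308 = 1.18 times as many as to Week 44. The on-treatment count is therefore a different quantity from either endpoint.

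**Use mixed with time observed.** Raw count = window × share of days with use.

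- Daily use, stops after two doses: 56 × 1.00 = 56 days, the most this patient can score.
- A completer passes 56 once the share exceeds 56/364 = 15.4%. At one day in four the completer scores 364 × 0.25 = 91.

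A Week 16 cut on its own, still limited to on-treatment time, would leave windows of 28 to 112 days. Hence the need for a diary-day denominator as well.

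**Can a direction between arms be derived?** The only relevant inputs in the documents are "a 15% dropout rate up to week 16 and a 30% dropout rate up to week 52", with no split by arm or reason. To see what the answer depends on, assume that lack-of-efficacy stoppers use rescue on 60% of days and stop on average at Day 114; that everyone else uses it on 25% (placebo) or 20% (fasinumab) of days; that other stoppers leave on average at Day 196; and that completers contribute 364 days. All of these are assumptions.

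Mean raw days = L × 0.60 × 114 + O × r × 196 + (1 − L − O) × r × 364. Mean share of days = L × 0.60 + (1 − L) × r. Here L and O are the fractions stopping for lack of efficacy and for other reasons, and r is 0.25 or 0.20.

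| L, placebo / fasinumab | O, placebo / fasinumab | Raw days, placebo / fasinumab (ratio) | Share of days, placebo / fasinumab (ratio) |
|---|---|---|---|
| 20% / 8% | 20% / 20% | 78.1 / 65.7 (0.84) | 0.320 / 0.232 (0.73) |
| 15% / 8% | 15% / 25% | 81.3 / 64.0 (0.79) | 0.3025 / 0.232 (0.77) |
| 10% / 6% | 15% / 25% | 82.4 / 64.1 (0.78) | 0.285 / 0.224 (0.79) |

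Ratios are fasinumab/placebo. In the first row the raw count understates the reduction on fasinumab, in the second the two measures nearly agree, and in the third the sign of the discrepancy reverses.

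**The case against.** The strongest reply has five parts.

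1. **The third rescue component is sound.** The weekly average is calculated for a specified week and divided by diary entries, so if it is tabulated by week it shows rescue use at Weeks 16 and 44 already adjusted for missing entries. This stands. A reader might infer that rescue use cannot be set beside the Week 16 pain result at all; the documents do not support that. But average mg gives neither the proportion of users nor the number of days.

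2. **No bias direction is shown.** A reader might infer that the raw count pulls the placebo comparison toward no difference, because placebo patients stop more often for lack of efficacy. The documents do not support that either. Protocol 7.3.2.1 requires stopping for adjudicated arthropathy, joint replacement, carpal tunnel symptoms and significant neuropathy, and protocol 1.1 and 1.2 describe joint and sensory events with fasinumab, so shorter fasinumab windows are also plausible. The table above shows the effect going either way. This stands in full.

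3. **Time on drug is already reported.** SAP 5.6.2 summarises SC exposure by arm, so unequal windows would be visible. This stands in part: arm-level exposure does not let a reader adjust patient-level counts, and exposure is not the number of diary days completed.

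4. **The endpoint is a count.** Replacing it with a percentage would change the endpoint. This stands, so the percentage belongs beside the count.

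5. **The stakes are low.** The endpoints are exploratory, the planned output is descriptive, and rescue use lies outside the multiplicity procedure in SAP 5.7.4. This stands, and it limits the weight of the point.

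**Conclusion.** The point holds for two of the three rescue components. Followed as written, SAP 5.7.5 does not yield the proportion of users or the number of rescue days to Week 16 or to Week 44. That conclusion rests on the text alone. The confounding of the day count with time observed rests only on the dosing schedule and arithmetic.

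No size or direction can be attached to a between-arm bias without stopping rates by arm and reason. The scenario ratios are illustrations from assumed inputs and should not be quoted as expected effects. The weekly mg average is largely protected, and no primary, key secondary or alpha-controlled result changes. This is a correction worth making before the analysis is run, to descriptive exploratory output.

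**What to change.** In SAP 5.7.5, Rescue Medications:

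- Derive the proportion using rescue and the number of rescue days separately for baseline to Week 16 and baseline to Week 44.
- Keep the count of days, since that is the protocol's endpoint, and beside it report rescue days as a percentage of completed diary days in the same window, with the number of diary days shown by arm.
- State whether diary entries made after study drug is stopped are counted. The endpoint definition does not exclude them, whereas the on-treatment window drops those later than four weeks after the last injection.

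The cost is a few lines of SAP text and two date cuts in the programming. Daily diary data are already collected to Week 52. The small downside is that the percentage treats days without a diary entry as unobserved, so it depends on why entries are missing; showing diary days by arm lets the reader judge that.

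### Year 1 rescue-medication days and weekly amount are summarised only among users, so the stated all-patient comparison is not presented directly and a treatment difference can be masked

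*SAP*

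**What the plan says.** Protocol Section 4.2.3 defines rescue endpoints comparing fasinumab with placebo and, separately, with naproxen: the proportion of patients taking rescue, "number of days on rescue medication, and weekly average use of rescue medication from baseline to weeks 16 and 44". SAP Section 4.5.3 repeats this almost word for word ("number of days on rescue medication, and weekly average use of rescue medication from baseline to week 16 and 44"). Neither limits the comparison to patients who took rescue.

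The analysis is under Rescue Medications in SAP Section 5.7.5 and has three parts:

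- **Proportion.** The number and percentage of users is given by treatment group on the safety set, first for the pre-treatment period. Then: "Analogous analysis will be performed for both the Year 1 On-Treatment Period and Year 2 On-Treatment Period".
- **Days.** "For patients taking rescue medication, descriptive statistics of the number of days patients took rescue medications will be presented by treatment group", again over the On-Treatment Periods.
- **Weekly amount.** "For patients taking rescue medication, weekly average usage of rescue medications (measured in mg) is calculated as follows": total mg in a given week divided by the "number of diary entries in the specified week". The display is descriptive: "Descriptive statistics of the weekly average usage of rescue medications will be presented by treatment group".

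No rule assigns zero to non-users, and Year 1 has no all-patient version of days or amount.

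Four other places bear on this. SAP Section 5.7 makes the mFAS the default for efficacy analyses unless stated otherwise; the rescue text states otherwise and uses SAF – Year 1 and SAF – Year 2. SAP Section 5.7.7 repeats the Section 5.7.5 analyses on the FAS. SAP Section 5 ends the Year 1 On-Treatment Period four weeks after the last Year 1 SC dose, or at the first Year 2 dose for those who continue. The Year 2 paragraph of SAP Section 5.7.6 lists rescue usage for summary on SAF – Year 2 with no users-only wording.

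**The concern.** Whether a patient takes any rescue medication is an outcome observed after randomization. If fasinumab relieves pain, some patients who would have used a little rescue will use none, and they leave the users-only table. Those left on fasinumab and those left on placebo are then selected differently, so a difference between their means is not a randomized comparison. A real reduction in rescue use can look smaller than it is or disappear, and under some usage patterns the sign can change.

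There is also a gap in the time windows. The endpoints run to Weeks 16 and 44, but the proportion and the days are summarised over an On-Treatment Period whose length varies by patient. Someone who stops injections early has fewer days in which to count rescue use, and no Week 16 or Week 44 cut is specified for these two measures.

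At stake is whether the exploratory rescue objective is answered in the form in which it is stated.

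**Working it through.** The documents give no rescue-use rates, days or mg, so there is no plan figure to reproduce. Every usage number below is an assumption chosen to show the mechanism.

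**Identity.** Let p be the proportion of users in an arm and m the mean among users. Non-users contribute zero, so:

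all-patient mean = p × m

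**When the users-only table misleads.** With F for fasinumab and P for placebo, the users-only mean is equal or higher on fasinumab while the all-patient mean is lower whenever

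1 ≤ m_F / m_P < p_P / p_F

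**Assumed cases.**

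| Case | Placebo: users, user mean, all-patient mean | Fasinumab: users, user mean, all-patient mean | Users-only difference | All-patient difference |
|---|---|---|---|---|
| A, days/week | 80%, 4, 3.2 | 60%, 4, 2.4 | 0 | −0.8 (25% lower) |
| B, days in period | 80%, 60, 48 | 50%, 60, 30 | 0 | −18 |
| C, days in period | 80%, 60, 48 | 40%, 90, 36 | +30 | −12 |

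Case C in full: on placebo 40% use 100 days, 40% use 20 days and 20% use none, so 0.4×100 + 0.4×20 = 48 and 48/0.8 = 60. On fasinumab the heavy users fall to 90 days and the light users to none, so 0.4×90 = 36 and 36/0.4 = 90.

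**Range.** With 80% users on placebo, the upper bound p_P / p_F on the user-mean ratio is:

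| Fasinumab users | 70% | 60% | 50% | 40% |
|---|---|---|---|---|
| Bound | 1.14 | 1.33 | 1.60 | 2.00 |

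If nearly everyone uses rescue the problem shrinks: at 95% and 90% users the bound is 0.95/0.90 = 1.06.

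**What can be recovered from the planned tables.**

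- Mean of days: yes, as p × m, provided the percentage and the user mean refer to the same patients and period. In case A, 0.60×4 = 2.4 and 0.80×4 = 3.2.
- SD of days: not presented, but derivable by hand from the users' SD s, since variance = p·s² + p(1−p)·m².
- Median and quartiles: in general no. With 80% users, the all-patient median is the users' (0.50 − 0.20)/0.80 = 37.5th percentile, which is not among the statistics that SAP Section 5 lists.
- Weekly mg: no direct figure. The SAP does not say whether the users are those who took rescue at any time in the period or those who took it in that week. On the first reading only never-users' zeros are lost; on the second every zero week is lost, and no weekly percentage of users is planned with which to restore it. Zeros are dropped either way.

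**Windows.** Weekly amount is defined for a specified week, so results for the weeks up to 16 and 44 are compatible with the text. Days and proportion are tied to the On-Treatment Period only.

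**The case against.** The plan is a two-part summary: how many used rescue, then how much the users took. A reader might infer that it would show no difference in case A. It would not, because the 60% and 80% would stand beside the equal user means, and the all-patient mean follows by multiplication. That stands, and it limits the harm.

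A reader might also infer that the users-only mean will point the wrong way. The documents do not support that. Reversal needs particular usage patterns, such as case C, and no rates are given. Rescue was also allowed for headache, other pain and fever (Protocol Section 7.2), so never-users over 52 weeks may be few. This is an inference too, but a fair one, and if it is right the effect is small on the period reading.

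Nor is it right that no as-randomized version exists. SAP Section 5.7.7 repeats the analyses on the FAS, which is by allocated treatment and limits Q8W contrasts to concurrently randomized patients. It does not lift the users-only restriction, and no mFAS version is named.

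Finally, these endpoints are exploratory, described without tests, and outside the 29 hypotheses of Protocol Section 10.1. A reader might infer that the primary result is affected. It is not: the primary estimand in SAP Section 5.7.1 includes data whether or not rescue was taken, and rescue is barred in the 24 hours before visits.

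**Conclusion.** The point holds at modest severity, mainly for Year 1, where the placebo comparison lies. Days and weekly mg are restricted to users, whereas the endpoints compare arms without that restriction. The contrast is therefore not between randomized groups and can mask an all-patient difference; reversal is possible only under assumed patterns. No size can be taken from the documents. In the assumed cases, all-patient reductions of 25% and of 18 days both appear as zero in the users-only means.

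The window gap is established for days and for the proportion of users, not for weekly amount. For Year 2, SAP Sections 5.7.5 and 5.7.6 do not agree on whether the summary is limited to users, so the defect is less certain there. No primary or key secondary conclusion depends on any of this.

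**What to change.** In SAP Section 5.7.5, for Year 1:

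- Summarise days and weekly mg for all patients in the analysis set with diary data, scoring zero for non-use. State that a day without an entry is missing rather than zero. Keep the users-only table as a supplement, and say whether users are defined by period or by week.
- Report the proportion of users and the days to Week 16 and to Week 44.
- Present by randomized arm on the mFAS, the default under SAP Section 5.7, with the FAS version that Section 5.7.7 already provides. Limit Q8W contrasts to concurrently randomized patients.

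For Year 2, reconcile the rescue text of Section 5.7.5 with the Year 2 paragraph of Section 5.7.6.

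The cost is a few lines of SAP text and re-run tables. Rescue use is already recorded daily in the diaries (Protocol Section 7.2), so no new data are needed.
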